4.3 Premature Subject Termination from the Study

4.3.1 Criteria

No subject initiating therapy in this trial will be replaced.

Any subject may be prematurely terminated from additional allergen exposures, but maintained on longitudinal follow-up for the following reasons:

• Anaphylaxis resulting in hypotension, neurological compromise or mechanical ventilation secondary to Baked Egg or Egg OIT dosing or any egg food challenge.

Any subject deemed to have severe symptoms and receives aggressive therapy at any time should be discontinued from further therapy, including the following:

- Poor control or persistent activation of secondary atopic disease (e.g., AD, asthma).
- Started on ARBs, ACE inhibitors, beta-blockers, or other prohibited meds and there are no alternative meds available per the prescribing doctor, they will be removed from further treatment.
- Pregnancy.
- Egg OIT Group subjects:
 - Circumstances (e.g., concurrent illness, such as gastroenteritis) requiring missed Egg OIT maintenance dosing of >7 consecutive days (this does not include subjects intentionally removed from therapy to administer an OFC off therapy).
 - Non-adherence with home Egg OIT dosing protocol (excessive missed days; i.e., >3 consecutive days missed on 3 occasions), would be a safety issue warranting discontinuation.

Any subject may be prematurely terminated from the study if:

- The subject elects to withdraw consent from all future study activities, including followup.
- The subject is "lost to follow-up" (i.e., no further follow-up is possible because attempts to reestablish contact with the subject have failed).
- The subject has biopsy documented Eosinophilic Esophagitis (EoE).

• The subject dies.

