The action is to continue the normal dosing at home but to confirm the food item that resulted in the symptoms as being appropriate or to have the subject return to clinic for an observed dose.

If moderate symptoms occur, defined as:

Skin - systemic hives/swelling

Respiratory – throat tightness without hoarseness, persistent cough, wheezing without dyspnea

GI – persistent moderate abdominal pain/cramping/nausea, increased vomiting

The action is to have the subject return to clinic for an observed dose with the appropriate baked food prepared in the clinic.

If symptoms resolve a careful review of the appropriate food preparation will be performed and dosing can continue at home.

If greater than mild symptoms occur with the in-clinic dose, then consultation with the Study Chair or Co-Chair as listed on the cover page of the protocol is warranted to determine the next course of action. The Study Chair or Co-Chair will be available for questions and decision making for any questions related to the study protocol from 10 AM ET to 5 PM ET during the working week.

If more *severe symptoms* occur, defined as:

Respiratory - laryngeal edema, throat tightness with hoarseness, wheezing with dyspnea

GI - significant severe abdominal pain/cramping/repetitive vomiting

The action is to have the subject return to clinic for an observed dose with the appropriate baked food prepared in the clinic.

If symptoms resolve, a careful review of the appropriate food preparation will be performed and the subject would return the next day for an observed dose prior to resuming dosing.

If greater than mild symptoms occur with the in-clinic dose, dosing will be stopped and the subject will be removed from further Baked Egg dosing. If oral pharyngeal or mild symptoms occur with the clinic dose then consultation with the Study Chair or Co-Chair as listed on the cover page of the protocol is warranted to determine the next course of action. The Study Chair or Co-Chair will be available for questions and decision making for any questions related to the study protocol from 8 AM ET to 5 PM ET during the working week.

6.4.1 Treatment for reactions to Baked Egg Dosing

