Treatment of individual reactions should be with either an antihistamine and/or epinephrine, along with IV fluids, albuterol, and steroids as indicated. Generally, for mild and moderate symptoms, the subject should receive antihistamines, and for more severe symptoms, the subjects should receive epinephrine, antihistamines, and then the other medications as indicated. If severe anaphylaxis to egg resulting in hypotension, neurological compromise or mechanical ventilation occurs at any time secondary to baked egg, the subject will be prematurely terminated from dosing.

Antihistamines

If a subject receives antihistamines only, the dosing can be continued.

Epinephrine

If epinephrine is used at home for a baked egg dose, the subject will be brought into clinic for an observed dose with the baked egg product prepared in-clinic. Any individual reaction that requires 2 or more doses of epinephrine (in clinic or at home) counts towards the stopping rules for the protocol.

Egg OIT:

Initial Dose Escalation - the initial day will be done at the Clinical Research Center (or equivalent monitored clinic setting) and consist of Egg OIT dosing, beginning at 0.1 mg egg white solid with graduated doses every 30 minutes up to 25 mg (if tolerated) on Day 1. The Egg OIT assignment group (that failed the baked egg challenge) will only escalate to 12 mg egg white solid maximum on Day 1. Subjects will not have active wheezing or a current flare of atopic dermatitis. If symptoms occur preventing escalation to 25 mg (12 mg in the Egg OIT assigned group), the highest tolerated dose (at least 3 mg) will be accepted as the "desensitization" dose for further escalation (See Exhibit 1, Section 6). The maximum tolerated dose on Day 1 (e.g., 3 mg, 6 mg, 12 mg, or 25 mg egg white solid) will be given on Day 2 as a single dose under observation at the Clinical Research Center. If moderate symptoms occur on Day 2, the subject will return to the Clinical Research Center on Day 3 for the next lower dose (must be at least 3 mg) under direct observation. If moderate symptoms re-occur, consultation with the Study Chair or Co-Chair is warranted to determine the next course of action. If symptoms prevent initial escalation desensitization dosing to 3 mg, the subject will be dropped from active treatment due to desensitization failure and followed longitudinally. Subjects tolerating 3 mg, 6 mg, or 12 mg egg white solid will go home to remain on that dose daily and

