Process algorithm for symptoms during build-up phase for Egg OIT (pre or post 1 year 7444 mg egg white protein OFC). (See Section 6, Exhibit 2)

Subjects will be free from active wheezing or a flare of atopic dermatitis prior to any dose escalation. Subjects will be maintained on their current dose of study product until their flare of asthma or atopic dermatitis resolve. Subjects may develop symptoms during dosing for the build-up phase. The investigator's judgment will be required to determine the best course of action with possible actions being the following:

- 1. Continue with daily home dosing.
- 2. Continue the same daily dose for the rest of the 2 week interval.
- 3. Return for repeat dosing in Clinical Research Center.
- 4. Return for dosing of previously tolerated dose (without escalation) in Clinical Research Center.
- 5. Discontinuation of dosing.

If a subject has a dose escalation in the Clinical Research Center without symptoms, the action should be to continue per protocol with daily home dosing of the tolerated dose with the next escalation visit to the Clinical Research Center 2 weeks later.

If the subject only experiences oral/pharyngeal pruritus during the administration of the daily dose, then the same dose can be repeated the next day at home and continued throughout the interval unless other symptoms begin to develop (see below).

For *mild symptoms*, defined as:

Skin – limited or localized hives/swelling, skin flushing or pruritus

Respiratory - rhinorrhea/ sneezing, nasal congestion, occasional cough, throat discomfort

GI - mild abdominal discomfort/ minor episode of vomiting

The action should be either to repeat the dose the next day (Day 2) at home or to have the subject return to the Clinical Research Center the next day (Day 2) for a repeat of the previous day's dose or the last tolerated dose (at the physician's discretion). If the dose is tolerated, then the subject will continue on that dose and return at the normal interval. If the dose causes mild symptoms again, then the subject may return to the Clinical Research Center (Day 3) and be given the last tolerated dose or a 1-2 step dose reduction. If tolerated, the subject will continue on this dose for the normal time interval. If mild symptoms recur, a 1-2 step reduction should be administered the next day (Day 4). If tolerated then that dose should be continued for 2 weeks. If not tolerated, consultation with the study chair should be indicated.

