If a subject fails dose escalation after three consecutive (with 2-4 weeks between) attempts, he/she will be considered a dose escalation failure and the last tolerated dose will be accepted as the maintenance dose. For a completed dose escalation with no symptoms, subjects should be observed for 30 minutes. For mild symptoms, subjects should have a 1-2 hours post-protocol observation period. For moderate to severe symptoms, the observation period should be at least 4 hours and up to 24 hours based on symptoms and treatment regimen needed to stabilize the subject.

Any subject deemed to have severe symptoms including hypoxia, hypotension or change in mental status (stage 3 defined in Appendix 3) and receives aggressive therapy at any time should be discussed with the Study Chair or Co-Chair and discontinued from active therapy.

For specific questions related to dosing escalation or continuation of the same dose that are not answered in the above protocol, the Study Chair or Co-Chair will be available for questions and decision-making.

Any subject who discontinues build-up dosing due to repeated allergic reactions to the egg product will have his/her mechanistic blood drawn within approximately 1 week of discontinuation of therapy.

6.4.2 Treatment for reactions during the Build-Up and Maintenance Phases

Treatment of individual reactions should be with either an antihistamine and/or epinephrine, along with IV fluids, albuterol, and steroids as indicated. Generally, for mild and moderate symptoms, the subject should receive antihistamines, and for more severe symptoms, the subjects should receive epinephrine, antihistamines, and then the other medications as indicated. If severe anaphylaxis (stage 3 defined in Appendix 3) occurs at any time, dose escalation will stop and the dose will be reduced to the last tolerated dose (must be at least 350 mg egg white solid) and the subject continued on that dose as long-term maintenance without further escalation.

Antihistamines

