If a subject receives antihistamines only, the dose escalation can be continued. If symptoms during a build up day require antihistamines in multiple doses or in combination with other medications (except epinephrine), there should be a dose reduction by 1-2 doses with the next dose given in the CRC. If dose escalation fails or requires treatment after 2 more escalation attempts each spaced 2 to 4 weeks apart, the dose should be reduced to the last tolerated dose (must be at least 350 mg egg white solid to continue) and continued long term without further escalation.

Epinephrine

Any reaction (in clinic or at home) that requires 2 or more doses of epinephrine counts towards the stopping rules for the protocol. Further dose escalation would not occur in this individual and maintenance on the last tolerated dose (must be greater than 350 mg) would be maintained.

Clinic

If a single administration of epinephrine is required during in clinic escalation, the dose should be reduced by 2 doses, and the subject continued on that dose for 4 weeks. After 4 weeks at the reduced dose, an escalation attempt may be tried in clinic.

If a single administration of epinephrine is required a second consecutive time during this escalation attempt, the dose should be reduced by 2 doses, and the subject continues on that dose for 6-8 weeks. After 6-8 weeks at the reduced dose, an escalation attempt may be tried in clinic.

If a single administration of epinephrine is required a third consecutive time during this escalation attempt, the dose should be reduced by 2 doses (if the reduced dose is at least 350 mg egg white solid) and the subject continued on that dose as long-term maintenance without further escalation.

Home

If a single administration of epinephrine use occurs during dosing at home, this epinephrine use is not counted as one of the uses described above, unless severe anaphylaxis occurs at home. The subject should return to clinic for an observed dose prior to resuming any dosing at home. The investigator may or may not decide to dose reduce depending on the specific circumstances surrounding the reaction.

MAINTENANCE PHASE (PRE 1 YEAR 7444 MG EGG WHITE PROTEIN OFC PHASE)

This phase consists of the subject receiving the maximum achieved daily dose of either baked egg or egg white solid OIT (as described above) for at least 8 weeks at home. The subject will continue to follow an egg-restricted diet for the duration of the study.

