For any noted symptoms during the maintenance phase, the same general study dosing rules for the build-up phase will be followed. Dosing reductions during the maintenance phase will be determined by the investigator based on the circumstances surrounding the reaction and subsequent dosing reactions.

Both Treatment Groups:

One year 7444 mg egg white protein OFC (at the conclusion of the initial build-up and initial maintenance phase) - All subjects will undergo a 7444 mg egg white protein OFC at 52 weeks after reaching the maximum achieved daily dose for 8 weeks as described above. Even though subjects initially may not tolerate more than approximately 2 gm of baked egg protein or 350 mg of egg white solid, long-term administration of egg may result in the capacity to tolerate much higher doses, and indeed 80% of individuals on 300 mg of egg white solid maintenance therapy for 24 months were "protected" and passed a 10 gm OFC.³⁷

All subjects who did not reach the maximum maintenance dose of Egg OIT will resume build-up starting at their current maintenance dose and stopping at the maximum maintenance dose or earlier if symptoms prevent further build-up. The doses administered and parameters for build-up

in the post 1 year 7444 mg egg white protein OFC phase will be identical to those in build-up prior to the 1 year 7444 mg egg white protein OFC.

Long Term Maintenance:

The year 2 maintenance portion of the study is to determine if the Baked Egg and/or Egg OIT can induce the development of sustained unresponsiveness to egg. Subjects in the treatment arm will remain on a daily dose of Baked Egg or Egg OIT (or resume build-up to reach the maximum maintenance dose as described above at least 4 weeks prior to the 2 year 7444 mg egg white protein OFC).

Subjects on each arm of the study will be followed with visits at 4 months (Visit 05) and 8 months (Visit 06) after the 1 year 7444 mg egg white protein OFC. At these visits, serum for egg-specific IgE and IgG4 will be obtained (up to 10 mL). Subjects will be called monthly to assess for dosing compliance, symptoms and a targeted history.

Missed Baked Egg Doses:

Baked Egg subjects will be encouraged to take the daily baked egg dose. Missed doses will be monitored for compliance through daily dosing diaries.

Missed Egg OIT Doses at any Phase of the Study:

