Appendix 3. Anaphylaxis Staging System

Staging System of Severity of Anaphylaxis					
Stage	Defined By				
1. Mild (skin & subcutaneous tissues, GI, &/or mild respiratory)	Flushing, urticaria, periorbital or facial angioedema; mild dyspnea, wheeze or upper respiratory symptoms; mild abdominal pain and/or emesis				
2. Moderate (mild symptoms + features suggesting moderate respiratory, cardiovascular or GI symptoms)	Marked dysphagia, hoarseness and/or stridor; shortness of breath , wheezing & retractions; crampy abdominal pain, recurrent vomiting and/or diarrhea; and/or mild dizziness				
3. Severe (hypoxia, hypotension, or neurological compromise)	Cyanosis or $\text{SpO}_2 \leq 92\%$ at any stage, hypotension, confusion, collapse, loss of consciousness; or incontinence				

Staging System of Severity of Anaphylaxis

Criteria for Diagnosis

Anaphylaxis is likely when any 1 of the three following sets of criteria are fulfilled:

- 1. Acute onset of an illness (minutes to hours) with involvement of:
 - Skin/mucosal tissue (e.g., *generalized* hives, itch or flush, swollen lips/tongue/uvula) AND
 - Airway compromise (e.g., dyspnea, stridor, wheeze/ bronchospasm, hypoxia, reduced PEF) AND/OR
 - Reduced BP or associated symptoms (e.g., hypotonia, syncope, incontinence)
- 2. Two or more of the following that occur rapidly after exposure to the allergen (minutes to hours):
 - Skin/mucosal tissue (e.g., generalized hives, itch/flush, swollen lips/tongue/uvula)
 - Airway compromise (e.g., dyspnea, stridor wheeze/bronchospasm, hypoxia, reduced PEF)
 - Reduced BP or associated symptoms (e.g., hypotonia, syncope, incontinence)
 - *Persistent* GI symptoms (e.g., nausea, vomiting, crampy abdominal pain)
- 3. Reduced BP after exposure to the allergen (minutes to hours):
 - Infants and Children: low systolic BP (age-specific) or > 30% drop in systolic BP*
 - Adults: systolic BP < 90 mm Hg or > 30% drop from their baseline

* Low systolic BP for children is defined as < 70 mmHg from 1 month to 1 year; less than (70 mmHg + [2 x age]) from 1-10 years; and < 90 mmHg from age 11-17 years.

** Isolated skin or mucosal lesions following the ingestion of a food constitute a "food-induced allergic reaction".

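### The mandatory Baked Egg stop in Section 6.4.1 omits hypoxia, a stage 3 sign in Appendix 3, and the Baked Egg re-dosing rules carry no stage 3 exclusion

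*Protocol*

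**What the plan says.** **General rule.** Protocol Section 4.3.1 covers both arms: "Any subject deemed to have severe symptoms and receives aggressive therapy at any time should be discontinued from further therapy". Aggressive therapy is not defined. The sentence then runs on into a list of other reasons: atopic disease control, prohibited drugs, pregnancy and missed Egg OIT doses. A separate bullet says a subject may be terminated from allergen exposure for anaphylaxis with low blood pressure, neurological compromise or ventilation.

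**Baked Egg severe path (Section 6.4, Reactions to Baked Egg Dosing).** Severe symptoms are defined by respiratory signs, including wheezing accompanied by dyspnea, and by severe gastrointestinal signs. The action is a dose observed in clinic. If symptoms resolve and food preparation has been reviewed, "the subject would return the next day for an observed dose prior to resuming dosing". More than mild symptoms on the clinic dose end Baked Egg dosing. Oral or mild symptoms require consultation with the Study Chair or Co-Chair.

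**Baked Egg treatment and stop (Section 6.4.1).** Severe symptoms are treated with epinephrine, antihistamines and other drugs. Epinephrine used at home leads to an observed clinic dose. Dosing ends without condition only in this case: "If severe anaphylaxis to egg resulting in hypotension, neurological compromise or mechanical ventilation occurs at any time secondary to baked egg".

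**Severity scale (Appendix 3).** Stage 3 is headed "Severe (hypoxia, hypotension, or neurological compromise", and its definition includes cyanosis or an SpO2 of 92% or less. The study-level stopping rule in Section 3.3 refers to this appendix.

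**Egg OIT build-up algorithm (Section 6.4).** Discontinuation applies to any subject with "severe symptoms including hypoxia, hypotension or change in mental status (stage 3 defined in Appendix 3) and receives aggressive therapy".

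**The concern.** A child who wheezes, is short of breath and has an SpO2 of 92% or less has stage 3 anaphylaxis under Appendix 3. The reaction counts toward suspending enrollment under Section 3.3. Yet a site that opens the Baked Egg part of Section 6.4 finds this child's presenting symptoms on a list whose action is another dose of the allergen. When the site then checks the mandatory stop in Section 6.4.1, hypoxia is not on it. At stake is whether a child is given egg again after a hypoxic reaction, and whether five sites would answer alike.

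**Working it through.** No figure in the plan bears on this point, so the main check is a comparison of texts.

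**1. Which outcomes each rule names**

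| Rule | Hypoxia | Hypotension | Neurological | Ventilation |
|---|---|---|---|---|
| Appendix 3, stage 3 | yes | yes | yes | not named |
| Egg OIT build-up algorithm, discontinue | yes | yes | yes | not named |
| Section 6.4.1, Baked Egg mandatory stop | **no** | yes | yes | yes |
| Section 4.3.1, permissive anaphylaxis bullet | **no** | yes | yes | yes |

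Stage 3 minus the Section 6.4.1 list leaves exactly one item: hypoxia.

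**2. Where a hypoxic Baked Egg child lands**
- Wheezing with dyspnea meets the Section 6.4 severe definition: observed re-dose.
- Epinephrine at home meets the Section 6.4.1 epinephrine rule: observed re-dose.
- Hypoxia without low blood pressure, neurological compromise or ventilation does not meet the Section 6.4.1 stop.
- Severe symptoms with aggressive treatment meet Section 4.3.1: discontinue.

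Neither re-dosing rule excludes stage 3 reactions, so the child can fall under both instructions.

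**3. What closing the gap could cost the primary analysis**

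Inputs: 96 randomized 1:1, so 48 per arm; 40% versus 70%; two-sided 5% chi-square (Protocol 9.3, SAP 5 and 8.3.1). A stopped child does not reach the off-therapy challenge and counts as a failure (SAP 3.3). The number of extra children stopped, 1 or 2, is an assumption.

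- Planned power, normal approximation with pooled variance under the null: SE0 = sqrt(2 × 0.55 × 0.45 / 48) = 0.1016; SE1 = sqrt((0.40 × 0.60 + 0.70 × 0.30) / 48) = 0.0968; z = (0.30 − 1.96 × 0.1016) / 0.0968 = 1.04, giving 85.1%. This reproduces the stated 85%.
- Largest shift, if each stopped child would have succeeded: 1/48 = 2.1 points; 2/48 = 4.2 points. Against the planned 30-point difference: 2.1/30 = 7%; 4.2/30 = 14%.
- Average shift, if each had a 40% chance of success: 0.40/48 = 0.8 points; 0.80/48 = 1.7 points, or 3% and 6% of the difference.
- Power at the average shift: a Baked Egg rate of 39.2% gives 87.1%; 38.3% gives 88.8%.
- Uncorrected chi-square near the design rates, against 34/48: 19/48 gives 9.48, p = 0.0021; 18/48 gives 10.74, p = 0.0010; 17/48 gives 12.09, p = 0.0005.

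These figures describe a side effect of the fix. They do not measure how often the problem arises.

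**The case against.** The strongest reply is that other text already protects the hypoxic child. Section 4.3.1 covers every subject, and Section 6.4.1 prescribes epinephrine and further drugs for severe symptoms, so a hypoxic child left without aggressive treatment is implausible. The build-up rule naming hypoxia may also reach Baked Egg: the maintenance phase covers "the maximum achieved daily dose of either baked egg or egg white solid OIT", and "For any noted symptoms during the maintenance phase, the same general study dosing rules for the build-up phase will be followed". Section 7.4.2 leaves removal to the investigator's judgment. This stands in part: the child is not unprotected. But Section 4.3.1 relies on an undefined term, and the build-up rule sits under a heading that begins "Process algorithm for symptoms during build-up phase for Egg OIT", so its reach to Baked Egg is by inference.

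It can also be said that re-dosing is reasoned and guarded. Section 6.4 calls Baked Egg reactions rare and often due to faulty preparation, and these children have passed a 2 g baked egg challenge. The three-item list recurs in the synopsis, Section 4.2 and Section 4.3.1, so it may be a deliberate threshold. That supports observed re-dosing after lesser reactions. It does not explain why the stop for a dosing reaction is narrower than the protocol's own definition of severe anaphylaxis, and no reason is given.

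Finally, Section 6.4.2 lets an Egg OIT subject continue at a reduced dose after stage 3, so a stage 3 stop for Baked Egg treats the arms differently. It does, but Sections 6.4.1 and 6.4.2 already differ in this way for hypotension and neurological compromise. The change extends that difference to hypoxia.

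A reader might infer a general conflict between Section 4.3.1 and the Section 6.4 severe path. The documents do not support that as a finding. Section 4.3.1 requires aggressive therapy as well as severe symptoms, and its scope is blurred by the unrelated list that follows. If its severity is read as the near-identical build-up sentence defines it (stage 3), most of the overlap disappears.

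**Conclusion.** The point holds in a narrow form and is minor. Hypoxia is the one Appendix 3 stage 3 feature missing from the mandatory Baked Egg stop, and two re-dosing rules lack a stage 3 exclusion. It would be too strong to say that the protocol expressly permits re-dosing after hypoxia: the Section 6.4 severe list never mentions it, and Section 4.3.1 would stop an aggressively treated child. The risk is divergent handling when a site works from the Baked Egg text alone. Its frequency cannot be estimated from the documents. The trial's conclusion is not threatened. On the assumption of one or two extra stops, the effect on the primary comparison is small and slightly favors Egg OIT.

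**What to change.** 1. In Section 6.4.1, replace the three-outcome trigger for ending Baked Egg dosing with: *stage 3 anaphylaxis (Appendix 3) or mechanical ventilation*.
2. In the Section 6.4 Baked Egg severe path and in the Section 6.4.1 home-epinephrine rule, add: *Re-dosing does not apply to stage 3 reactions (Appendix 3), which are discontinued under 6.4.1.*

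Leave Section 4.3.1 as written. Narrowing it to stage 3 would weaken protection for other aggressively treated reactions, such as laryngeal edema. The remaining overlap for those reactions is not resolved by this change.

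The cost is one replaced phrase, two added sentences, the amendment approvals in Section 11.1 and a site memo. A rare additional Baked Egg child would be stopped and counted as a primary-endpoint failure. Sample size, visits and analysis do not change.
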